### 10.3.1.7. Adverse Event and Serious Adverse Event Follow-Up

All AEs and SAEs should be followed until resolution, return to baseline, or until the point it is deemed that further recovery is unlikely. All measures required for AE management and the ultimate outcome of the AE will be recorded in the source document and AE CRF module.

#### 10.3.1.8. 7.1.8. Ongoing Safety Evaluation

A study safety evaluation will be conducted on a regular (monthly) basis by teleconference. Dose exposure, dose-limiting toxicity, AE/SAE profiles and clinical laboratory abnormalities, and other safety measures will be reviewed during each convened meeting. Subject accrual will not be interrupted during the regular scheduled safety evaluations. These discussions will be led by the Spirita Oncology Medical Monitor and Principal Investigator.

### **10.4.** Efficacy Assessments

Efficacy assessments will be determined on the basis of MRI and/or CT scans with best treatment response at any protocol-specified time point for intracranial disease, duration of response, duration of stable disease, and time to intracranial lesion disease progression. Response rates also will be determined for non-CNS systemic disease. Progression-free survival (PFS) and overall survival (OS) will be evaluated.

Confidential 55
December 31, 2019 Protocol Amendment 4

#### 10.4.1. Efficacy Endpoints

#### 10.4.1.1. Primary Efficacy Endpoint

The primary efficacy endpoint is the proportion of subjects with intracranial OR following E6201 plus dabrafenib treatment. OR for subjects with CNS metastases from metastatic melanoma include a best response of CR or PR, as defined by RECIST v.1.1 (APPENDIX E) and RANO-BM (APPENDIX F).

#### 10.4.1.2. Secondary Efficacy Endpoints

To evaluate intracranial disease duration of response, duration of SD and time to progression of CNS metastases, progression-free survival and overall survival, as defined below:

- Duration of Response: length of time from the first evidence of objective response (CR, PR) of intracranial disease lesions to the first objective evidence of progression
- Duration of Stable Disease: length of time from first evidence of stable disease of intracranial disease lesions (CR, PR, SD) to for objective evidence of disease progression or death, whichever is earlier
- Time to Progression of CNS Metastases: length of time from date of first administration of study drug to first objective evidence of disease progression of intracranial lesions
- Progression-Free Survival: length of time from the date of first administration of study drug to the first objective evidence of disease progression or death, whichever is earlier
- Overall Survival: length of time from the date of first administration of study drug to the date of death from any cause.

#### 10.4.2. Timing of Assessments to Determine Objective Response

Disease assessments will be made at the end of Cycle 2 every even numbered cycle thereafter. Disease assessments may be made at other time points at the discretion of the Investigator.

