Blood for hematology and serum chemistry determinations will be collected within 28 days of Cycle 1 Day 1 and on Day 1 of each cycle and at the End of Treatment Visit.

ECGs will be taken within 28 days prior to Cycle 1 Day 1, pre-infusion and 5 minutes following the end of the E6201 2-hour infusion, on Day 1 of every cycle thereafter, and at the End-of-Study visit.

CNS and non-CNS systemic disease assessments will be based on magnetic resonance image (MRI) or computed tomography (CT) if unable to perform MRI for intracranial disease. Assessments will be obtained at Week 8 and every 8 weeks thereafter until documented progression of disease (PD). Subjects who demonstrate clinical benefit will be allowed to continue therapy until progression of disease, observation of unacceptable adverse events, intercurrent illness or changes in the subject's condition that prevents further study participation.

Safety will be assessed through the monitoring of adverse events (AEs), clinical laboratory parameters (hematology and serum chemistry), vital sign measurements, ECGs and physical examinations. Adverse events will be classified according to the Medical Dictionary for Regulatory Affairs (MedDRA) and graded according to the National Cancer Institute Common Terminology Criteria for Adverse Events (NCI CTCAE) version 4.03.

Efficacy assessments will be determined on the basis of MRI and/or CT scans with best treatment response at any protocol-specified time point for intracranial disease, duration of response, duration of stable disease, and time to CNS metastasis disease progression based on RECIST v.1.1 and RANO-BM. Response rates also will be determined for non-CNS systemic disease. Progression-free survival (PFS) and overall survival (OS) will be evaluated.

A correlation will be made between *BRAF* mutational status (e.g., type, heterozygosity or homozygosity) in archival tissue with clinical outcome.

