#### 5.5.1.3. Schedule Adjustments for Toxicity

• Dosing delays are permitted for either E6201 or dabrafenib. Once a toxicity has resolved to ≤ Grade 1, the subject may resume treatment. The dose level must be reduced to the next lower dose level when treatment is re- initiated following a delay for drug-related toxicity unless otherwise specified.

• The maximum delay allowed between treatment cycles for either E6201 or dabrafenib is 2 weeks. If toxicity has not resolved after 2 weeks of delay, the Medical Monitor should be contacted to discuss permission for resuming treatment after a longer delay for subjects who are experiencing clinical benefit.

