## 9.3. Requirements During Treatment Cycles After Cycle 1 (Cycle 2 and beyond) [± 3 days]

- Abbreviated physical examination (Day 1 only)
- Vital signs
- ECOG Performance Status
- Weight (Day 1)
- The following lab tests:
  - Hematology, if not performed within previous 24 hours

Confidential 47
December 31, 2019 Protocol Amendment 4

- Serum chemistry, if not performed within previous 24 hours
- E6201 study drug administration (Days 1, 4, 8, 11, 15 and 18)
- Continue dabrafenib twice daily treatment
- Review Dabrafenib Patient Medication Diary with subject (applicable to Combination Phases of study only)
- 12-lead ECG pre-dose, at 5 minutes after the infusion ends ( $\pm$  5 minutes)
- Review of concomitant medications
- Assessment of adverse events
- Assessment for survival
- CT or MRI of systemic and intracranial disease for re-staging (Day 28 of even numbered cycles, ± 7 days)

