## APPENDIX D. SCHEDULE OF STUDY PROCEDURES

Study Activity	Screening a	Treatment Cycle 1		Treatment Cycles after Cycle 1		Progression or Relapse	End of Treatment l	Long-Term Follow-Up n	
		Day 1	Day 8 i	Day 15 i	Day 1	End of Cycle 2 j,k			
Signed ICD	X								
Medical History	X								
Physical Examination	X	X			X h			X	
Vital Signs	X	X	X	X	X			X	
ECOG Perform. Status	X	X	X	X	X			X	
Height	X								
Weight	X	X			X			X	
Hematology b	X	X			X			X	
Serum Chemistry c	X	X			X			X	
Beta-hCG for WCBP	X								
12-lead ECG	X	X d			X d			X	
Concomitant Medications	X	Continuous							
AE Assessment		Continuous							
Disease Assessment e	X					X	X		
E6201 Administration f		X (+D4)	X (+D11)	X (+D18)	X (D 1, 4, 8, 11, 15, 18)				
Dabrafenib Dosing g,m		X	X	X	X			X m	
Assessment of Survival		X			X	X	X	X	X

- a Screening to be performed within 28 days of Cycle 1, Day 1
- b Hematology parameters collected at Screening, Cycle 1 Day 1 (only if not performed in the previous 24 hours), Day 1 of each subsequent cycle (within 3 days of Day 1 of each subsequent cycle) and End of Treatment. See Table 9 for tests to be conducted at each time point.
- c Serum chemistry collected at Screening, Cycle 1 Day 1 (only if not performed within the previous 24 hours), Day 1 of each subsequent cycle (within 3 days of Day 1 of each subsequent cycle) and End of Treatment. See Table 9 for tests to be conducted at each time point.
- d ECGs performed pre-dose and at the end of the E6201 2-hour infusion (± 5 minutes)
- e Disease Assessment may include CT, MRI, and/or physical exam
- f E6201 IV twice weekly Day 1,4, 8, 11, 15 and 18 of each 28-day cycle
- g Dabrafenib dose orally twice daily, continuously. Provide Dabrafenib Patient Medication Diary.
- h Abbreviated physical exam
- i Day 8, 15 ( $\pm 1$  day)
- j Day 28 (±7 days)
- k Perform at the end of every even numbered cycle thereafter
-  End of Treatment visit should be within 28 days from last dose of study medication (±5 days)
- m Review Dabrafenib Patient Medication Diary (each clinic visit + End of Treatment)
- n Long-term follow-up for 6 months consists of clinic visits or telephone calls every 3 months to assess survival status

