## 2.5. Frequency of tumor re-evaluation

Frequency of tumor re-evaluation while on treatment should be protocol specific and adapted to the type and schedule of treatment. However, in the context of phase II studies where the beneficial effect of therapy is not known, follow-up every 6–8 weeks (timed to coincide with the end of a cycle) is reasonable. Smaller or greater time intervals than these could be justified in specific regimens or circumstances. The protocol should specify which organ sites are to be evaluated at baseline (usually those most likely to be involved with metastatic disease for the tumor type under study) and how often evaluations are repeated. Normally, all target and non-target sites are evaluated at each assessment. In selected circumstances, certain non-target organs may be evaluated less frequently. For example, bone scans may need to be repeated only when complete response is identified in target disease or when progression in bone is suspected.

After the end of the treatment, the need for repetitive tumor evaluations depends on whether the trial has as a goal the response rate or the time to an event (progression/death). If 'time to an event' (e.g. time to progression, disease-free survival, progression-free survival) is the main endpoint of the study, then routine scheduled re-evaluation of protocol specified sites of disease is warranted. In randomized comparative trials in particular, the scheduled assessments should be performed as identified on a calendar schedule (for example: every 6–8 weeks on treatment or every 3–4 months after treatment) and should not be affected by delays in therapy, drug holidays or any other events that might lead to imbalance in a treatment arm in the timing of disease assessment.

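### Scans are scheduled by calendar week in one place and by cycle end in another, and nothing says which rule governs once a cycle is delayed or dosing stops before progression

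*Combined protocol and SAP*

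**What the plan says.** Two scheduling rules are in force.

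- **Calendar rule.** Section 5.1: "Assessments will be obtained at Week 8 and every 8 weeks thereafter until documented progression of disease (PD"). The synopsis says the same.
- **Cycle rule.** Section 10.4.2: "Disease assessments will be made at the end of Cycle 2 every even numbered cycle thereafter". Section 9.3 lists "CT or MRI of systemic and intracranial disease for re-staging (Day 28 of even numbered cycles, ± 7 days"). A footnote to Appendix D reads "Perform at the end of every even numbered cycle thereafter".

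Section 5.5.1.3 makes the difference matter: "The maximum delay allowed between treatment cycles for either E6201 or dabrafenib is 2 weeks". If toxicity has not resolved by then, "the Medical Monitor should be contacted to discuss permission for resuming treatment after a longer delay"; that extension is for subjects with clinical benefit. Section 10.4.2 also permits, but does not require, extra assessments at the investigator's discretion.

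Sections 10.4.1.2 and 11.3.2.2 date PFS and CNS time to progression from first dose to the first evidence of progression (or death, for PFS). The End of Treatment list in 9.5 contains no imaging, and long-term follow-up in 9.6 covers survival only.

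**The concern.** Outside of death, progression is known only when a scan shows it, so the scan calendar is part of the definition of PFS, CNS time to progression, and duration of response and stable disease. Appendix E, section 2.6.3, itself notes that follow-up frequency influences such measures. If scan dates follow cycle dates, and cycle dates slip because of toxicity, scan timing depends on how the subject tolerates treatment. Two sites could scan identical subjects on different dates and both claim compliance.

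The second gap concerns subjects who stop dosing without progression. They have no further cycles, so the cycle rule calls for no more scans, although 5.1 says scans continue until documented progression. This can happen: section 3.4.1 reports that one of the four monotherapy subjects left because of an adverse event and not progressive disease. Section 11.3.2.2 censors subjects without progression at the last follow-up time and does not tie that to the last scan. Read literally, follow-up without scans could count as progression-free time.

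**Working it through.** **Inputs.** Cycle length 28 days, or 4 weeks (Appendix D: "E6201 IV twice weekly Day 1,4, 8, 11, 15 and 18 of each 28-day cycle"). Calendar scans at Weeks 8, 16, 24 and so on (5.1). Cycle scans at the end of Cycles 2, 4, 6 and so on, ±7 days (9.3, Appendix D). Delay of up to 2 weeks at a cycle boundary (5.5.1.3).

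**Step 1: the rules agree without delay.** End of cycle c = 4c weeks. Cycle 2 ends at 2 × 28 = 56 days = Week 8, and Cycle 4 at Week 16.

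**Step 2: scan dates with delay.** With d weeks of delay at every boundary, end of cycle c = 4c + d(c − 1). For d = 2: Cycle 2 gives 8 + 2 = 10, Cycle 4 gives 16 + 6 = 22, Cycle 6 gives 24 + 10 = 34.

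| Scan | Calendar rule | Cycle rule, one 2-week delay before Cycle 2 | Cycle rule, 2-week delay at every boundary |
|---|---|---|---|
| Cycle 2 | Week 8 | 10 | 10 |
| Cycle 4 | 16 | 18 | 22 |
| Cycle 6 | 24 | 26 | 34 |
| Cycle 8 | 32 | 34 | 46 |

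Section 5.1 gives no window. If ±7 days is borrowed from 9.3, the calendar window for the first scan is Weeks 7 to 9. A nominal Week 10 scan lies outside it; the cycle window (Weeks 9 to 11) touches it only at Week 9. A delay of a week or less can be absorbed.

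**Step 3: direction in an individual.** Take one 2-week delay before Cycle 2. Progression by Week 8 is recorded at Week 10 instead of 8 (+2). In each later 8-week interval, progression in the first 2 weeks is recorded 6 weeks earlier (true Week 9 is seen at Week 10 instead of 16), and progression in the remaining 6 weeks is recorded 2 weeks later. If e is the share of subjects recorded earlier, the mean shift is 2(1 − e) − 6e = 2 − 8e.

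**Step 4: average size.** The documents give no expected PFS, so I assume exponential progression times with medians m of 8 to 36 weeks. With s(t) = 2^(−t/m), e = s(8)[1 − s(2)] / [1 − s(8)].

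- m = 8: s(8) = 0.5, s(2) = 0.841, e = 0.159, mean shift 2 − 8 × 0.159 = 0.73 weeks.
- m = 36: s(8) = 0.857, s(2) = 0.962, e = 0.227, mean shift about 0.19 weeks.

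A simulation of 400,000 subjects at medians 8, 12, 16, 24 and 36, taking recorded progression as the first scan at or after true progression, agrees (0.72 and 0.19) and covers other delay patterns:

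| Delay pattern under the cycle rule | Mean shift against the calendar rule (weeks) |
|---|---|
| One 2-week delay before Cycle 2 | 0.19 to 0.72 |
| 2-week delay at 10% of boundaries | 0.21 to 0.23 |
| 2-week delay at 25% of boundaries | 0.51 to 0.56 |
| 2-week delay at 50% of boundaries | 0.98 to 1.07 |
| 2-week delay at every boundary | 1.79 to 1.95 |

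With one early delay, 77% to 84% of subjects are recorded later and 16% to 23% earlier. With a delay at every boundary, 70% to 79% are later and 21% to 30% earlier. The model has no deaths, discretionary scans or delays beyond 2 weeks. I report means because recorded medians sit on scan dates and move in jumps.

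**The case against.** A reader might infer that the cycle rule lengthens PFS in every delayed subject, by as much as 6 weeks. The documents do not support that. Six weeks is the displacement of the Cycle 4 scan when the maximum delay occurs at all three preceding boundaries. It is not a typical bias, and the protocol gives no delay frequency. Table 4 ends E6201 after a third Grade 3 or a second Grade 4 related event, so three successive E6201-driven delays fit mainly repeated Grade 2 events. Step 3 shows that some progressions are recorded earlier.

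A reader might also take Appendix E, section 2.5, to forbid cycle-timed scanning, because it says calendar assessments "should not be affected by delays in therapy, drug holidays or any other events". That sentence is addressed to randomized comparative trials in particular, and its stated worry is imbalance between arms. This trial is non-randomized. The same section accepts phase II scans timed to cycle ends, and ties routine scanning after treatment to trials whose main endpoint is a time to event. Here the primary endpoint is intracranial response.

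Other mitigation is fair to note. Section 10.4.2 allows discretionary scans, 9.4 lists an assessment at progression, and deaths counted in PFS keep their own dates. The affected endpoints are summarised by Kaplan-Meier with no test or comparator.

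All of this limits the size of the problem. It does not settle which of the two rules governs a delayed subject, or who scans a subject who has stopped dosing without progression.

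**Conclusion.** This is a real but minor inconsistency. The two rules coincide only while cycles run on time, and no text resolves them otherwise. In delayed subjects, recorded PFS and CNS time to progression can shift either way. The average shift is later, by about 0.2 to 2 weeks across the patterns examined. That range rests on assumed exponential medians of 8 to 36 weeks and on delays of no more than 2 weeks per boundary; the longer delays that may be permitted are not covered. Discretionary scans would reduce it. The primary response rate, and the decision rule on responses in 18 subjects, are little affected. The missing scans after dosing stops without progression are a separate contradiction with 5.1, and their size cannot be estimated from the documents. The case for acting is that the correction is cheap and removes toxicity-dependent timing from endpoints dated by scans.

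**What to change.** Reconcile 9.3, 10.4.2 and Appendix D to the schedule in 5.1 with one sentence: disease assessment every 8 weeks (±7 days) counted from Cycle 1 Day 1, regardless of dose delays, until documented progression. Put the same window in 5.1 and the synopsis. Amend 9.5 and 9.6 so that subjects who stop treatment without progression stay on that schedule; changing only the on-treatment sections would leave this gap open.

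Cost: wording in those sections. Nothing changes for subjects whose cycles run on time, and the scan frequency is the one 5.1 already requires. In delayed subjects scans may no longer fall on cycle visits, and off-treatment scans that 5.1 already implies must be scheduled. No dose or treatment rule is touched.

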#### 10.5. Pharmacodynamic Assessment

A correlation will be made between *BRAF* mutational status (e.g., type, heterozygosity or homozygosity) in archival tissue with clinical outcome.

Confidential 56
December 31, 2019 Protocol Amendment 4

#### 11. STATISTICAL METHODOLOGY

#### 11.1. **Determination of Sample Size**

The statistical objective is the evaluation of the intracranial disease OR rate, defined as CR or PR, on treatment with E6201 plus dabrafenib. The sample size is based on a one-arm binomial design  $H_0 \le 0.05$  ( $\le 5\%$  response rate for historical control group) versus  $H_1 > 0.05$  (> 5% response rate for experimental group). An objective response rate (OR) of 25% or greater is deemed clinically important. A total of 3 or more responses in a sample size of 18 subjects indicates the true OR rate is  $\geq 25\%$ , with power = 80%, alpha = 0.05, and provides evidence of clinical utility to move forward.

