Dose-limiting toxicity (DLT) is defined as any one of the following events:

- Grade 4 hematologic toxicity for > 1 day
- Grade 3 hematologic toxicity with complications (e.g., thrombocytopenia with bleeding)
- Failure of Grade 3 thrombocytopenia, absolute neutrophil count (ANC), hemoglobin to recover to Grade ≤ 1 within 4 weeks despite the use of platelet and red blood cell (RBC) transfusions and/or growth factors

Confidential 30
December 31, 2019 Protocol Amendment 4

• ≥ Grade 3 non-hematologic toxicity not due to disease progression (excluding Grade 3 nausea, vomiting or diarrhea that is adequately controlled with supportive care and resolves to ≤ Grade 2 within 48 hours, or Grade 3 electrolyte disturbances responsive to correction within 24 hours)

- ≥ Grade 3 liver function tests (LFTs) lasting > 72 hours
- Treatment interruption > 14 days due to toxicity
- Other important medical event

Subjects who require a dose reduction due to toxicity will be considered to have had a DLT.

If a DLT is experienced in  $\geq 2$  of 6 subjects in the Combination Safety Run-in Phase during Cycle 1, no further subjects will be enrolled at that dose level. Subjects who experience a DLT may continue treatment at the next lower dose level until disease progression or unacceptable toxicity. The MTD is defined as the doses of E6201 plus dabrafenib at which  $\leq 1$  of 6 subjects experiences a DLT.

E6201 dose reductions for suspected E6201-related toxicity will be 240 mg/m^2 twice weekly (Dose Level -1) and 160 mg/m^2 twice weekly (Dose Level -2), administered over the same schedule as above, Days 1, 4, 8, 11, 15 and 18, repeated every 28 days.

Dabrafenib dose reductions for suspected dabrafenib-related toxicity will be 100 mg (Dose Level -1), 75 mg (Dose Level -2) and 50 mg (Dose Level -3) orally twice daily, according to the U.S. Product Label.

A total of 6 subjects will be treated at the combined MTD doses for both drugs established in the Combination Safety Run-in Phase before beginning the Expansion Phase.

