Expansion Phase: Following screening, an additional cohort of up to N=18 subjects will be treated at the E6201 plus dabrafenib combined MTD. Subjects treated at the MTD in the Combination Safety Run-in Phase will count towards accrual in the Expansion Phase. E6201 will be administered by IV infusion over a 2-hour period at the MTD and schedule determined in the Combination Safety Run-in phase, repeated every 28 days (=1 cycle), and dabrafenib will be administered orally twice daily at the MTD determined in the Combined Safety Run-in phase. Both regimens will be subject to dose reductions for toxicity, as described. Subjects who demonstrate clinical benefit (objective response or stable disease) will be allowed to continue therapy with E6201 plus dabrafenib until progression of disease, observation of unacceptable adverse events, intercurrent illness or changes in the subject's condition that prevents further study participation.

During the study, a Safety Review Committee (SRC), consisting of the actively recruiting investigators, the Sponsor Medical Monitor and study staff will review data from the Monotherapy and Combination Safety Run-in Phases before beginning the Expansion Phase, and will review data from the Expansion Phase on an ongoing basis.

The statistical objective is the evaluation of the intracranial disease objective response (OR) rate, defined as complete response (CR) or partial response (PR), on treatment with E6201 plus dabrafenib. The sample size is based on a one-arm binomial design  $H_0 \le 0.05$  ( $\le 5\%$  response rate for historical control group) versus  $H_1 > 0.05$  (> 5% response rate for experimental group). An objective response (OR) rate of 25% or greater is deemed clinically important. A total of 3 or more

Confidential 31
December 31, 2019 Protocol Amendment 4

responses in a sample size of 18 subjects indicates the true OR rate is  $\geq$  25%, with power of = 80%, alpha = 0.05, and provides evidence of clinical utility to move forward.

CNS disease response will be assessed according to 2 methodologies: Response Evaluation Criteria in Solid Tumors (RECIST v. 1.1). and Response Assessment in Neuro-Oncology – Brain Metastases (RANO-BM). Clinical benefit is defined as best response of CR), (PR) or stable disease (SD).

Non-CNS systemic disease will be assessed according to RECIST v. 1.1.

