# **5.2.** Number of Subjects and Centers

A total of 4 subjects were enrolled in the Monotherapy Safety Run-in Phase. A total of 6-12 subjects are anticipated in the Combination Safety Run-in Phase. A total of up to 18 subjects will be enrolled in the Expansion Phase for a total of N=28-34 for the study. Study centers include University of Arizona ([name]), and additional study centers as needed to ensure timely accrual to the study.

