#### 11.3.2. Efficacy Analysis

#### 11.3.2.1. Primary Efficacy Endpoint

The primary efficacy endpoint is the proportion of subjects with intracranial OR following E6201 plus dabrafenib treatment. Intracranial response rates will be summarized using number and percentage of subjects with a best response of CR, PR, SD or PD assessed by RECIST v. 1.1 and RANO-BM, along with 2-sided, 95% confidence intervals for the proportions.

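### The rule of 3 or more responses in 18 has exact one-sided alpha 0.058 and power 86.5%, not 0.05 and 80%, and meeting it does not show a true response rate of at least 25%

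*Combined protocol and SAP*

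**What the plan says.** Section 11.1 describes a one-arm binomial design that tests an intracranial objective response rate of 5% or less (the historical control figure) against a rate above 5%. A rate of 25% or more is called clinically important. The decision rule follows: "A total of 3 or more responses in a sample size of 18 subjects indicates the true OR rate is" at least 25%, "with power = 80%, alpha = 0.05, and provides evidence of clinical utility to move forward". The Synopsis (Methodology) and section 5.1 repeat the rule and its figures. None of the three places calls the figures nominal or approximate, or says whether they come from an exact calculation. The test direction is implied by the alternative hypothesis but not named.

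Section 11.3.2.1 summarises response as counts and percentages "along with 2-sided, 95% confidence intervals for the proportions", without naming an interval method.

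On who makes up the 18, section 5.1 says "an additional cohort of up to N=18 subjects will be treated at the E6201 plus dabrafenib combined MTD", and its next sentence says "Subjects treated at the MTD in the Combination Safety Run-in Phase will count towards accrual in the Expansion Phase". The same section says "A total of 6 subjects will be treated at the combined MTD doses for both drugs" before the Expansion Phase begins. Section 5.2 says "A total of up to 18 subjects will be enrolled in the Expansion Phase for a total of N=28-34 for the study".

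**The concern.** This is the trial's only numerical efficacy criterion for moving forward, and two things in it look wrong.

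First, a test of a 5% null cannot establish a rate of 25%. In this design 25% is the rate at which power is calculated; it is not a value that rejection supports. Read literally, a trial with exactly 3 responders would be reported as showing a clinically important rate, although its observed rate of 16.7% is itself below 25%.

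Second, with 18 subjects the attainable binomial error rates move in large steps, so a cut-off of 3 landing on both 0.05 and 80% would be a coincidence that needs checking.

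A related problem is that the 18 subjects on whom the rule is read are not clearly identified.

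**Working it through.** **Inputs** (section 11.1): n = 18, success if X is 3 or more, null rate 0.05, rate of interest 0.25. I take the test as one-sided because the alternative is a rate above 5%.

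**Can the plan's figures be reproduced?** N = 18 can. The one-sided arcsine formula is n = [(1.645 + 0.842) / h]², with h = 2·arcsin(√0.25) − 2·arcsin(√0.05) = 1.047 − 0.451 = 0.596. It gives n = 17.4, rounded up to 18, and power 81.2% at 18. A one-sided normal approximation with continuity correction gives 17.7, also 18. That either method was used is my assumption. Neither gives the properties of the cut-off of 3.

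**Exact properties of the rule.** P(X ≥ 3) = 1 − P(0) − P(1) − P(2).

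- At 5%: 1 − 0.3972 − 0.3763 − 0.1683 = 0.058 (0.0581 unrounded), against a stated 0.05.
- At 25%: 1 − 0.0056 − 0.0338 − 0.0958 = 0.865 (0.8647 unrounded), against a stated 0.80.

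The next cut-off, 4 or more of 18, gives alpha 0.0109 and power 69.4%. No cut-off at n = 18 therefore meets both stated figures.

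**How often the rule is met at rates below 25%.**

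| True rate | P(3 or more of 18) |
|---|---|
| 5% | 5.8% |
| 10% | 26.6% |
| 15% | 52.0% |
| 20% | 72.9% |
| 25% | 86.5% |

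**What exactly 3 of 18 shows.** The observed rate is 3/18 = 16.7%. The exact one-sided p-value against 5% is 0.058, and the exact one-sided 95% lower bound is 4.7%. To exclude rates up to 25% at one-sided 0.05 would take 9 responders: P(X ≥ 8 | 0.25) = 0.057 and P(X ≥ 9 | 0.25) = 0.019.

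**Two-sided 95% intervals at 3/18.**

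| Method | Interval | Contains 5%? |
|---|---|---|
| Clopper-Pearson | 3.6% to 41.4% | yes |
| Wald (lower limit truncated at 0) | 0% to 33.9% | yes |
| Wilson | 5.8% to 39.2% | no |
| Agresti-Coull | 5.01% to 40.0% | no |

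All four contain 25% and values well below it.

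**Who the 18 are.** The planned total is 4 + 6 + 18 = 28 to 4 + 12 + 18 = 34, which leaves no overlap between the run-in and the Expansion Phase. If the 6 run-in subjects at the MTD are among the 18, only 12 more are needed, and the total is 4 + 6 + 12 = 22 to 4 + 12 + 12 = 28. Without overlap, 6 + 18 = 24 subjects would be treated at the MTD. Nothing in the plan applies the cut-off of 3 to 24 subjects; if that were done, alpha would be 0.116.

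**The case against.** The numerical discrepancy is small. Alpha is over by 0.8 percentage points, power is higher than claimed, and this is a Phase 1 study whose efficacy results are to be summarised as percentages with intervals. The design is also described as binomial with a directional alternative, so little is missing about the test. This stands as far as it goes, and it is why the error rates are the lesser part of the point. It does not rescue the 25% conclusion, which fails whatever calculation method or sidedness is assumed.

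A second objection is that calling 3 of 18 evidence of a rate above 5% sits badly with a lower bound of 4.7%. That is fair if the level is left unstated: 3 of 18 does not reject at 0.05. The replacement sentence must therefore carry the 0.058 level.

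Third, a nearby exact design does meet both stated figures: 3 or more of 16 has alpha 0.043 and power 80.3%. That is an alternative open to the sponsor, but the plan can be corrected without it.

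Finally, the plan gives the confidence interval no decision role, so the unnamed method is missing detail and not an error. I accept that. The overlap in the subject counts is a separate matter from the arithmetic, but it is a real contradiction and bears on the denominator of the rule.

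**Conclusion.** The concern holds. The rule of 3 or more in 18 has exact one-sided alpha 0.058 and power 86.5%, against the stated 0.05 and 80%. Meeting it supports at most a rate above 5%. It is passed about half the time at a true rate of 15% and nearly three quarters of the time at 20%, both below the plan's own threshold of clinical importance. The unsupported conclusion is the main fault; the alpha and power figures are a modest misstatement.

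The alpha comparison assumes a one-sided test, as the direction of the alternative implies; a two-sided reading of 0.05 would make the excess larger. The passages on the run-in and Expansion subjects also conflict: the planned total is 28 to 34 without overlap, or 22 to 28 with it. This should be fixed, but it does not stop the trial from running.

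**What to change.** In the Synopsis, section 5.1 and section 11.1, keep the cut-off of 3 in 18 and restate it along these lines: *three or more responses in 18 subjects will be taken as evidence that the objective response rate exceeds 5% (exact one-sided alpha 0.058 at 5%; power 86% at a true rate of 25%)*. Delete the statement that the rule indicates a rate of 25% or more.

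In the Synopsis and sections 5.1 and 5.2, reconcile the additional cohort of up to 18 and the total of 28 to 34 with the sentence that counts run-in subjects at the MTD towards the Expansion Phase, and state which 18 subjects the rule is read on.

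Two details could be settled in the same edit, though their absence is not an error: the interval method in section 11.3.2.1 and whether the interval has any decision role; and whether subjects replaced under section 6.3.2 stay in the denominator. If Clopper-Pearson is chosen, note that 3/18 does not exclude 5% whereas 4/18 (6.4% to 47.6%) does.

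Restating the rule costs wording only: no added patients and no change to the cut-off, at the price of a slightly less favourable alpha and a more modest conclusion. Reconciling the counts also needs only text, but the sponsor must say which planned total is intended.
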